9.2 Comparable Methods

We will use established and validated assays for determination of changes in biomarkers expression in this study. We plan to evaluate biomarkers in serum, tissue and DNA for secondary endpoints evaluation.

As to the primary endpoint, the method has been validated and already described in peer-reviewed publications (52).

For secondary serum biomarkers we will utilize standardized protocols of commercially available kits already described in peer-reviewed publications. Standard control samples as well as an in-house pooled serum sample will be analyzed in each run to monitor for inter- and intra assay coefficient of variation. We will pair samples obtained from the same participant (pre and post-treatment) and run samples in batches to reduce analytical variability. As to SHBG (28,53), HOMA index (53,54) and adipokines (37,55) our group has already published several papers involving these biomarkers.

10. SPECIMEN MANAGEMENT

10.1 Laboratories

Planned analysis of biomarkers will be centralized to specialized laboratories as outlined below.

10.1.1 Blood samples

Specimen (amount)	Laboratory
Serum 1 aliquot (1 mL) Estradiol, Estrone and estrone-sulfate levels	[name] Quest Diagnostics Nichols Institute
Serum 1 aliquot (1 mL) Ultra sensitive estradiol levels	inVentiv Health, Princeton, NJ
Serum, 6 aliquots (1 mL each) Androstenedione, Testosterone, SHBG levels and Insulin levels Adiponectin and Leptin levels	[name], PhD Division of Cancer Prevention and Genetics European Institute of Oncology
Serum 1 aliquot (1 mL) EXE and 17-dihydroEXE Levels	[name], MD, PhD Director, Laboratory Medicine and Pathology Haukeland University Hospital and University of Bergen
Serum 1 aliquot (1 mL) Proteomic Biomarker Discovery	[name] Proteomics Shared Resource Herbert Irving Comprehensive Cancer Center Columbia University Medical Center
Whole Blood EDTA-treated, 2 aliquots (1 mL each) DNA extraction and UGT2B17 copy number variation analysis	[name], PhD Division of Cancer Prevention and Genetics European Institute of Oncology

10.1.2 Tissue samples

Specimen	Laboratory
Tru-cut Biopsy 1 (FFPE) – Italian Sites Histological evaluation prior to randomization	Pathology staff at institution where diagnosis was performed
Tru-cut FFPE sections from Biopsy 1 – Italian Sites Six consecutive 5-micron thick sections from FFPE tru-cut biopsy for centralized analyses of Ki67 (and ER, PGR HER2)	[name], MD Division of Pathology European Institute of Oncology
FFPE block or 6 unstained slides from the initial diagnostic biopsy – US Sites	[name], MD Division of Pathology European Institute of Oncology
Surgical specimen 1: Breast Tumor Tissue (FFPE) Histological evaluation of surgical specimen	Pathology staff at each institution where definitive diagnosis was performed
Surgical specimen 1: FFPE sections from breast tumor Six consecutive 5-micron thick sections from each FFPE block mounted on charged slides [preferably within 7 days prior to shipping]	[name], MD Division of Pathology European Institute of Oncology
Surgical specimen 2: Flash Frozen Breast Tumor (minimal wet weight: 200 mg) Estradiol/exemestane measurements	[name], MD, PhD Director, Laboratory Medicine and Pathology Haukeland University Hospital and University of Bergen
Surgical specimen 3: Flash Frozen Normal Breast (minimal wet weight: 200 mg) Estradiol/exemestane measurements	
Surgical specimen 4: Flash Frozen Breast Tumor (minimal wet weight: 50 mg) Proteomic Biomarker Discovery US Sites only	[name] Proteomics Shared Resource Herbert Irving Comprehensive Cancer Center Columbia University Medical Center
Surgical specimen 5: FFPE sections from normal breast fat Crown like structures (IHC staining)	Potential Anxillary Study Investigator to be defined

The analysis of serum concentrations of estradiol, estrone and estrone-sulfate will be performed at the Quest Diagnostics Nichols Institute, San Juan Capistrano, CA, US under the supervision of [name].

The analysis of serum concentrations of ultrasensitive estradiol will be performed at inVentiv Health lab, Princeton, NJ, USA.

The analysis of serum concentrations of exemestane and its main metabolite 17-dihydroxy-exemestane will be performed by the Hormone Laboratory, Haukeland University, Bergen, Norway under the supervision of [name] MD, PhD.

The analysis of serum concentrations of androstenedione, testosterone, SHBG, insulin, adiponectin and leptin will be performed at the IEO Cancer Prevention Lab, Milan, Italy under the supervision of [name], MSC, PhD. The IEO Cancer Prevention Lab is also responsible DNA extraction, UGT2B17 copy number variation analysis, and for Centralized Biobanking of leftover specimens.

The evaluation of IHC biomarker analyses will be centralized to the Division of Pathology, IEO, Milan, Italy under the supervision of [name].

Proteomic profiling will be centralized to [name] Shared Resource for the Herbert Irving Comprehensive Cancer Center (HICCC) at Columbia University Medical Center (CUMC).

10.2 Collection and Handling Procedures

Specific instructions about specimen handling and storage will be provided in a separate Manual of Operations and Procedures.

10.2.1 Blood

It is strongly recommended for all blood samples for biomarkers to be drawn under fasting condition (at least 6 hours) preferably between 8 a.m. and 10 a.m. at baseline and the day of surgery (or the day before, depending on the local institutional procedures).

A total of **10 ml of blood** will be withdrawn for **safety lab exams and lipid profile** at baseline and before surgery.

At baseline and before surgery a total of **20 ml of blood** will be collected into vacuum blood collection tubes containing beads coated with clotting activator for **serum** separation to be employed for circulating **biomarker analysis**. Accordingly with specific tubes adopted at your hospital, please refer to the manufacture instructions. Allow the blood to clot at room temperature for 30 minutes. Then, spin in centrifuge for 10 minutes. Sarstedt Serum Monovettes tubes require 10 min centrifugation at 2000 x g at room temperature, while BD Vacutainer® SST™ and PST™ gel tubes should be spun at a speed of 1300 x g. Swing-out buckets best option for both systems. . After centrifugation, the yellow top layer, which corresponds to serum, is pipetted using the disposable transfer pipettes in 10 even aliquots (about 1.0 mL each) into the polypropylene cryotubes (Thermo Fisher Scientific), specifically labeled according to the Instructions in the Manual of Operations and Procedures. Tubes are tightly capped and stored in a dedicated – 80°C freezer equipped with a temperature control and temperature log chart or an alarm monitoring system per institutional standards.

At baseline and before surgery a total **3 ml whole blood** will be collected in tubes containing EDTA-K2 as anti-coagulant agent. The tube is gently mixed and blood is pipetted using disposable transfer pipettes in 2 even aliquots (about 1.5 mL each) into the polypropylene cryotubes (Thermo Fisher Scientific), specifically labeled according to the Instructions in the Manual of Operations and Procedures . Tubes are tightly capped and stored in a dedicated –80°C freezer equipped with a temperature control and

temperature log chart or an alarm monitoring system per institutional standards.

Specimen collection kits for storage of serum and blood samples will be provided by the Central Laboratory, at the Division of Cancer Prevention and Genetics, European Institute of Oncology in Milan, Italy (See the Instructions in the Manual of Operations and Procedures for requesting kits). Briefly, they will provide labels and polypropylene cryotubes and rack (Thermo Fisher Scientific) and instructions for specimen handling, processing, labeling, tracking and storage.

Each local site must be equipped with a -80°C (range -70 °C to -80 °C) freezer provided with temperature control 24 hours a day, 7 days a week and temperature log charts or an alarm monitoring system, better if electronic. The Center should also be equipped with a back-up freezer.

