7. CLINICAL EVALUATIONS AND PROCEDURES

7.1 Schedule of Events

The possibility of taking part in a pre-surgical trial will be presented to incoming postmenopausal women with a highly suspicious palpable lesion or a newly diagnosed ER-positive DCIS or breast cancer. The baseline visit will be scheduled for interested potential participants after histological confirmation.

SCHEDULE OF EVENTS

Evaluation/ Procedure	Screening Visit ¹	Baseline Visit/ Registration (within 14 days prior to randomization)	Randomization	Phone call (Day 1)	Phone call (1 week +3 days prior to surgery) ²	Final Visit (Days 28+1, 35+1, or 42+1) ³	Surgery (Days 29, 36 or 43) ¹²
Screening Informed Consent	X						
Tru-cut biopsy (Eligibility ER + breast cancer)	X						
Informed Consent		X					
Assess eligibility		X					
Medical history		X					
Physical exam/ height/weight/vital signs		X				X ^{9,10}	
Tobacco / alcohol use assessment		X					
Fasting blood lab tests ⁴		X				X	
Blood lab tests that may not be fasting ⁵		X				X ¹⁰	
Fasting blood for biomarkers ⁶		X				X	
Tissue for biomarkers (FFPE blocks or slides)		X					X
Frozen tissue for biomarkers							X
Frozen tissue for proteomics ¹¹							X ¹¹
Concomitant medications		X			X	X	
Baseline symptoms		X					
Confirm eligibility		(X)	X				
Randomization			X				
Dispense study agent ¹³			X ¹³				
Treatment initiation				X ⁷			
Collect study agent						X	X
Compliance					X	X	
Review agent diary/record						X	
Adverse events					X	X	
QoL questionnaire ⁸		X				X	

¹ For the Italian sites only

² If the participant is seen on site for the physical exam and blood safety tests on Day 7 prior to surgery, perform all procedures in person rather than as a phone call. In all other cases call the participant on the phone 1 week +3 days prior to surgery

³ Based on institutional procedure, the final visit may occur on the same day as surgery or the day before. The Final Visit must be

conducted on Days 28+1, 35+1, or 42+1.

⁴ **Fasting** blood lab tests (local lab): Glucose, total cholesterol, HDL cholesterol and triglycerides. Fasting is strongly recommended, but is not mandated. Every effort should be taken to draw these labs fasting.

⁵ Blood tests for safety that do not require fasting: complete blood count (CBC), AST, ALT, Na, K, BUN, total bilirubin, Cl, Ca, alkaline phosphatase, creatinine, and FSH if needed

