⁶ **Fasting** blood collection for biomarkers: estradiol, exemestane, 17-dihydroxyexemestane, estrone, estrone-sulphate, androstenedione, testosterone, SHBG, insulin, leptin, adiponectin. Fasting is strongly recommended, but is not mandated. Every effort should be taken to draw these labs fasting.

⁷ The first phone call is not performed if the day of call coincides with the day of the baseline visit

⁸ Quality of Life questionnaire

⁹ Do not repeat the height assessment at the Final Visit. Height measurement will be used from the baseline visit

¹⁰ May be done within 7 days prior to surgery or the day of surgery

¹¹ US Sites Only

¹² Surgery must occur on Days 29, 36 or 43. For this study coordinators are advised to count back from the day of surgery so that participants can either have 28, 35 or 42 days of study agent (ending on the 7th day of blister pack). Study agent can be dispensed in advance of starting agent on Day 1. However, coordinators must remind the participants not to start the study agent until the agent start date is provided to them by the coordinating center, in most cases via a telephone call from the coordinating site to the participant, indicating when to start the agent.

¹³ In person or by mail.

Unresolved AEs with a “possibly”, “probably” or “definitely” attribution to study agent at final visit will be monitored via telephone call at 20-30 days after surgery. AEs occurred after surgery will not be recorded.

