7.5 Evaluation at Completion of Study Intervention

At the final visit, participants will undergo physical exam, vital signs, and anthropometric measurements (weight, waist measurement, hip measurement). These procedures may be done **within 7 days prior to surgery or on the day of surgery**. Do not repeat the height assessment at the Final Visit. Height measurement will be used from the baseline visit.

Blood tests for safety that do not require fasting may be done **within 7 days prior to surgery or on the day of surgery**:

- complete blood count (CBC), AST, ALT, Na, K, BUN, total bilirubin, Cl, Ca, alkaline phosphatase, and creatinine

All other procedures are performed the day of surgery or the day before surgery:

Fasting blood lab tests that are performed at the local lab (glucose, total cholesterol, HDL cholesterol and triglycerides). Fasting is strongly recommended, but is not mandated. Every effort should be taken to draw these labs fasting.

Fasting blood for biomarkers will be collected. Fasting is strongly recommended, but is not mandated. Every effort should be taken to draw these labs fasting.

The date and time of blood draw, the date and time of surgery, and the date and time of last pill intake will be recorded.

The use of concomitant medications, adverse events, compliance, and quality of life assessment will be assessed. Study agent will be collected. A review of agent diary will be performed.

Any kind of surgery will be allowed from simple lumpectomy to total mastectomy. Tissue samples will be collected from the surgical specimen and processed according to Section 10. A detailed Manual of Operations and Procedures will be implemented with the specific procedures for each specimen.

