13.5 Secondary Objectives, Endpoints, Analysis Plans

We will attempt to understand the mechanism of action of exemestane on the primary endpoint of the study. More specifically, we will assess the effects of exemestane on the secondary endpoint biomarkers to see whether the effects of different doses on the primary endpoint is through the secondary endpoint biomarkers or independent of them. This will entail exploratory analysis of the primary endpoint by the secondary endpoint biomarkers while accounting for the effect of treatment.

Secondary objectives:

- To assess safety and toxicity.
- To support the preventive activity of exemestane we will investigate the change in Ki-67 and PgR level on the tumor adjacent intraepithelial neoplasia and/or grossly benign tissue.
- To assess possible association of estradiol level with tissue and circulating biomarkers.
- To investigate possible pharmacogenetic markers.
- To assess drug levels on tissue samples.
- To investigate tissue and circulating proteomics profiling.

Secondary endpoints:

- Exemestane safety and toxicity will be evaluated at the clinic visit according to the Common Terminology Criteria for Adverse Events v4.0 (CTCAE) and by a self-administered Quality of Life questionnaire (MENQOL).
- Change in Ki-67 expression comparing pre-treatment versus post-treatment specimen to compare the antiproliferative effect among the different dosages.
- Serum drug measurements of exemestane and 17-dihydroxyexemestane at the end of treatment.
- Additional validated method of estradiol measurement. This method has a lower detection limit (1 pg/ml) than the CLIA certified estradiol test (Quest) and will serve as a quality control since it has proven to more effectively detect estradiol concentrations at the very low level, which is characteristic of older postmenopausal women.
- Serum concentrations of estrone, estrone-sulfate, will be measured by LC-MS/MS while androstenedione and testosterone will be measured at baseline and at surgery. Sex hormone binding globulin serum levels will be measured by a chemiluminescent microparticle immunoassay (CMIA) on the ARCHITECT *i* System (Abbott Laboratories, Weisbaden, Germany).
- Change in concentrations of insulin, glucose (HOMA index) and lipid profile (total cholesterol, HDL cholesterol and triglycerides) will be evaluated.

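### Fasting is advised but not required and no fasting status is listed for recording, so any non-fasting samples would go unidentified and may distort the exploratory HOMA, insulin, glucose and triglyceride results

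*Combined protocol and SAP*

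**What the plan says.** Two blood collections feed these endpoints. The local panel covers "blood lab tests (local lab): Glucose, total cholesterol, HDL cholesterol and triglycerides" (section 7.1, footnotes). The biomarker sample carries insulin. Both are headed as fasting collections, and for both the footnotes add: "Fasting is strongly recommended, but is not mandated. Every effort should be taken to draw these labs fasting". Sections 3, 7.3 and 7.5 take the same position.

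Section 10.2.1 is the only place that gives a duration. It says "It is strongly recommended for all blood samples for biomarkers to be drawn under fasting condition", and the sentence goes on to define the condition and the preferred hours: "drawn under fasting condition (at least 6 hours) preferably between 8 a.m. and 10 a.m".

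Section 7.5 states which times are captured at the final visit: "The date and time of blood draw, the date and time of surgery, and the date and time of last pill intake will be recorded". Section 7.3, on the baseline visit, lists no times at all. Neither section mentions the last meal, hours fasted or a fasting yes/no item.

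Section 13.5 then lists "Change in concentrations of insulin, glucose (HOMA index) and lipid profile" among the secondary endpoints, with triglycerides part of that profile. Section 2.3 gives the purpose: to see whether the three dose schedules differ in their effect. The analysis plan in 13.5 uses ANCOVA on final values and on changes, adjusted for baseline, with age and BMI as examples of confounders. It also tabulates changes and percentage changes by arm. It declares all secondary analyses exploratory. The exclusions in 13.6 and 13.8 turn on eligibility, compliance and drop-out, not on fasting.

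**The concern.** HOMA is built from the product of glucose and insulin and is meant for fasting values. Triglycerides also depend on recent food. A plan that labels these as fasting tests, accepts non-fasting ones and lists nothing to tell them apart will pool the two kinds of sample. The analyst can then neither adjust for the difference nor check whether it matters.

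The two draws also take place in different settings. Baseline is a clinic visit within 14 days before randomization. The final draw is on the day of surgery or the day before, depending on the site. Fasting rates may therefore differ between the two, and any such difference would enter the planned tables of change from baseline. Meal times are hard to recover afterwards, so the gap is best closed while samples are being drawn.

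**Working it through.** The documents give no sample size, standard deviation or target effect for these four endpoints, so there is no figure of the plan's own to reproduce. The check has two parts.

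**What the text lists at each draw**

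| Item | Baseline (7.3) | Final visit (7.5) |
|---|---|---|
| Fasting required | No | No |
| Time of blood draw | Not listed | Listed |
| Time of last pill | Not applicable | Listed |
| Time of last food or fasting flag | Not listed | Not listed |
| Fasting term or rule in 13.5 | None | None |

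Section 5.2 asks for the tablet after dinner at about 8 PM, so the pill time hints at the evening meal. It says nothing about later food or breakfast, and there is no pill at baseline.

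**Illustration of size, for HOMA**

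Inputs:
- n = 54 per arm, from section 13.3. Every other input is an assumption.
- s = 0.40, the SD of the change in log HOMA when all samples are fasting.
- d = 0.5 to 1.0, the rise in log HOMA in a non-fasting sample. This is a factor of exp(0.5) = 1.65 to exp(1.0) = 2.72.
- f0 and f1, the non-fasting shares at baseline and at the final draw, independent between visits and equal across arms.
- Two-sided 5% test of one arm against another.

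*Step 1, spread.* SD of change = sqrt(s² + d²[f0(1 - f0) + f1(1 - f1)]).
- 5% at each visit, d = 0.5: sqrt(0.16 + 0.25 × 0.095) = 0.429, which is 1.07 times 0.40.
- 20% at each visit, d = 1.0: sqrt(0.16 + 1 × 0.32) = 0.693, which is 1.73 times 0.40.

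*Step 2, power between arms.* With all samples fasting, the difference detectable with 80% power is (1.960 + 0.842) × 0.40 × sqrt(2/54) = 0.216 on the log scale. For the same difference with the SD inflated by a factor r, power = Φ(2.802/r - 1.960).
- r = 1.07: power 0.74.
- r = 1.73: power 0.37.

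With equal shares across arms, the expected bias in the between-arm contrast is zero.

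*Step 3, shift in within-arm change.* Shift = exp[(f1 - f0)d] - 1.
- 20% at baseline, 5% before surgery, d = 0.5: exp(-0.075) - 1 = -7%.
- 30% at baseline, 5% before surgery, d = 1.0: exp(-0.25) - 1 = -22%.
- Equal shares at the two visits: no shift.

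*Step 4, one woman.* Suppose a non-fasting sample has insulin 2 to 3 times higher and glucose 20% higher. HOMA is then 2 × 1.2 = 2.4 to 3 × 1.2 = 3.6 times the fasting value. A woman fed at baseline and fasted at the end shows a false fall of 1 - 1/2.4 = 58% to 1 - 1/3.6 = 72%.

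Steps 1 to 3 use a change-score model. The planned ANCOVA would weight baseline differently, so the figures give the order of size only. Insulin, glucose and triglycerides alone would need their own shifts and are not modelled.

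**The case against.** The case against has several parts.

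- **The rate is unknown.** The protocol presses sites to draw fasting and prefers an early-morning window. Non-fasting samples may be rare. This stands, and it makes the harm conditional.
- **The comparison of interest is between randomized arms.** Participants and investigators are blinded to schedule (section 6.9), so there is no evident reason for fasting to differ by arm. This stands. A reader might infer that the dose comparison is biased, but the documents do not support that. What it stands to lose is precision. Bias is a risk for the within-arm changes, which 13.5 does plan to report.
- **The endpoints are exploratory.** Section 13.5 says so, and the primary estradiol conclusion does not depend on them. This stands and limits the weight of the point.
- **The case report forms and the Manual of Operations and Procedures are separate documents not available here.** They may already capture fasting status. That would remove the need for a new field, but 13.5 would still have no rule for using it.
- **The covariate list in 13.5 is open-ended.** Fasting status could be added as a confounder, but only if it is recorded.
- **Restricting the main analysis to women fasted at both draws would discard randomized women on a variable measured after randomization.** This is a fair objection to that remedy, so the restriction belongs in a sensitivity analysis.

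**Conclusion.** The point holds as a low-priority gap in data capture and analysis. The protocol permits non-fasting samples for HOMA, insulin, glucose and triglycerides, lists nothing that would identify them, and has no analysis rule for them. Such samples may therefore distort these exploratory endpoints.

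On the assumptions above, power for a HOMA contrast that would have 80% power with all samples fasting falls to between 0.74 and 0.37 with 5% to 20% non-fasting at each visit. Mean within-arm change shifts by about -7% to -22% if 20% to 30% are non-fasting at baseline and 5% before surgery. Only the 54 per arm comes from the documents. If almost all samples are fasting, both effects are negligible.

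Two stronger readings are not supported. A reader might infer that these endpoints are in fact distorted, but no non-fasting rate is given. A reader might also take the 58% to 72% false fall as a study-level effect. It describes one woman fed at baseline and fasted at the end, and would apply to an arm only if every woman in it followed that pattern.

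**What to change.** 1. Record time of last food at both draws, unless the case report forms already do. The advice on fasting itself can stay as it is.
2. In section 13.5, keep all randomized women with samples in the main ANCOVA for HOMA, insulin, glucose and triglycerides, and add fasting status at each draw as a covariate.
3. Prespecify a sensitivity analysis in women fasted at both draws. Use the 6-hour definition in section 10.2.1, and state that it also applies to the local glucose and triglyceride samples, for which no duration is given.
4. If enrolment has already begun, class earlier draws with no record as unknown.

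The cost is one data field, one short addition to the analysis plan, and a smaller sample in the sensitivity analysis. For draws already taken without a record, the gain is limited.
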